4.8 Statistical Analysis Plan

Our primary statistical approach is regression based, using a general linear model to conduct bivariate correlations, multiple linear regression, analysis of variance or covariance, as well as tests of mediation and/or moderation and a mixed-effect model for repeated measures (MMRM) recommended for primary analysis of clinical trials with continuous endpoints.⁽¹³⁶⁾ We will screen measures for violations of assumptions and use robust standard errors or power transformations if assumptions are not met. All regression-based analyses will be performed using either SAS software, version 9.4 (SAS Institute Inc., Cary, NC), or Stata, version 15.1⁽¹³⁷⁾ We will also adopt a discovery-based analysis of patient sub-groupings. This analysis will be based on an unsupervised clustering of all patients across all molecular measurements, with two primary outcomes. We will identify (1) patterns of molecular expression linking different

methylation profiles to gene and protein expression to evaluate the types of molecular signatures that discriminate sample groupings, and (2) sets of clinical covariates that are associated with sample sub-groups to determine the clinical and phenotypic factors that describe and differentiate sample clusters. These analyses will be performed using R software.

4.8.1 Evaluate Efficacy of ATVV

Aim 1: Evaluate the efficacy of daily ATVV among mothers with childhood adversity on behavioral and physical measures of M-I synchrony in a randomized study with an Attention Control group. The goal of our analysis is to determine treatment arm differences at the study endpoint (3 postnatal months), using a 2.5% type I error rate and two-sided test for our primary outcomes. We will use 5% type I error rate and Benjamini Hochberg correction among related groups of secondary outcomes.⁽¹⁴⁷⁾ We will estimate treatment effects with and without key covariates known to be associated with M-I synchrony (e.g., mental health, adversity, infant feeding method, infant health status, and 1-month Parenting Stress Index) which will increase the power of the test. For infant outcomes, we will include sex as a covariate and test for treatment effect differences by sex using an interaction term. Our statistical method for the physical measures, measured at baseline (late pregnancy) and monthly intervals (1-, 2-, and 3- postnatal months), will be MMRM regressing the outcome on indicators for treatment, time, and their interaction. For the physical measures the goal is to determine treatment arm differences in change from baseline to the study endpoint. In contrast, our method for the behavioral outcomes, measured once at the study endpoint, will be a general linear model regressing the outcome on an indicator for treatment arm. We will conduct intention to treat (ITT) and per protocol analyses (defined as completing 80% or more of daily ATVV sessions) and compare our findings. While missing data will be minimized through careful procedures, some missing data are inevitable with longitudinal studies. In order to retain all randomized participants for ITT, we will use multiple imputation to predict missing outcomes with all available measures, and model aggregated results across imputation datasets.⁽¹³⁸⁾ For physical measures where we have repeated measurements, we will compare multiple imputation results to the full information maximum likelihood approach available through MMRM. We will use inclusive models with auxiliary variables related to missingness, among covariates collected at baseline, if needed to support the missing at random assumption.^(138, 139) Sensitivity analyses will assess the robustness of our findings if we find imbalanced baseline characteristics in spite of randomization, characteristics associated with attrition, or non-ignorable missing data. We will conduct fidelity and dose response analyses in addition to our main effects models. Dose (frequency of ATVV sessions) will be collected daily for three months from the treatment arm participants and can be used to explore the patterns of adherence over time as well as optimal dose associated with OXT system changes by month.

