3.3 Outcomes

The two primary outcomes are mother-infant synchronous gaze and mother-infant synchronous affect. These and the secondary outcomes are listed in Table 2. Constructs and Operational Measures.

Table 2. Constructs and Operational Measures

Construct	Operational Measure	Time*			
		B/I	1	2	3
Outcomes					
OXTR epigenetic marks	Maternal plasma for % DNA methylation from candidate CpG sites -1001, -959, -934, -924, -901, and -860. Methylation relates to social, maternal nurturing behavior, & mRNA levels ⁽³⁸⁻⁴⁴⁾ CpG sites selected based on their implication in previous studies ^(46-50, 69) and cost-effectiveness in co-targeting additional regions using the selected assay.				
OXTR expression	Maternal plasma for mRNA level using qRT-PCR to report total OXTR gene expression (this reflects DNA transcribed [copied] into RNA, before translation produces protein).				
OXTR protein	Maternal plasma for total protein level of OXTR (amount of OXT receptors available to bind with OXT peptides) using Anti- OXTR antibody and Western Blot (gold standard).				
OXT peptide	ELISA assay to report OXT peptide level from maternal plasma and infant saliva. In our pilot, we collected sufficient infant saliva (1.5-2.0 ml) for the kit's sensitivity of 15pg/ml OXT detection. Antenatal and postnatal OXT measures are stable between groups. ⁽¹⁴⁰⁾				
Mother-Infant Synchrony	3-minute video-recording of mothers freely interacting with their infant and micro-coded for mother and infant gaze [primary], affect [primary], vocalization and touch.				

*Baseline (B), In-hospital (I), and postnatal months T1, T2, T3; **Available in Spanish

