4.7 Power Analysis

Our final sample size at the 3-month endpoint is estimated to be at least 100 per treatment arm, after a projected 20% attrition from enrollment of 250 women. This sample size will achieve 80% power to detect as significant a 0.44 standard deviation difference in primary outcomes (M-I synchrony gaze and affect) between treatment arms assuming $\alpha=0.025$ and a 2-sided test. Similar interventions on a related outcome (maternal sensitivity), and preliminary data from members of our team (on OXT level), showed between group effect sizes ranging from 0.28 to 0.62. In addition, the standardized differences in M-I synchrony ranged between 0.12 and 0.7 comparing at-risk (i.e., premature infants, maternal depression) and normal comparison groups at 3 and 9 months, supporting our choice of 0.4 as a feasible and clinically meaningful effect size. For aim 2 we have 80% power to detect modest correlations of 0.22 and larger assuming a conservative $\alpha=0.01$.

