7.0 Project Management

7.1 Timeline

The proposed research will require approximately four years to complete data collection. We will conduct preliminary analysis on available outcome data at the beginning of years 2 and 3. We have applied and received a no-cost-extension for final laboratory analyses, statistical analyses, and dissemination of findings. The quality of acquired data will be monitored frequently.

Table 4. General Timeline

	Year 1 by quarter				Year 2 by quarter				Year 3 by quarter				Year 4 by quarter				
	1	2	3	4	1	2	3	4	1	2	3	4	1	2	3	4	
Staff hiring & training, data set-up	□	□															
Data set up, entry, management, & cleaning	□	□	□	□		□	□	□	□	□	□	□		□	□	□	
Recruitment		□	□	□		□	□	□		□	□	□		□	□	□	
Data collection		□	□	□		□	□	□		□	□	□		□	□	□	
Blood & saliva processing		□	□	□		□	□	□		□	□	□		□	□	□	
Lab analysis of OXTR measures								□						□	□		
Lab analysis of plasma & saliva OXT peptide														□	□		
Coding of M-I synchrony videos									□	□				□	□		
Statistical analysis						□	□	□		□	□	□		□	□	□	
Preparation/dissemination of findings/reports									□	□	□	□		□	□	□	

Table 5. Detailed Timeline with No-Cost-Extension for Final Months of the Study

	10/1 2023	11/1 2023	12/1 2023	1/1 2024	2/1 2024	3/1 2024	4/1 2024	5/1 2024	6/1 2024	7/1 2024	8/1 2024	9/1 2024	10/1 2024 to 1/31 2025			
Baselines end	*															
Births end 2-10 weeks later		*	*													
T1 data collections end				*	*											
T2s data collections end					*	*										
T3s data collections end						*	*									
Bio samples to labs	*	*	*	*	*	*	*	*								
Collect birth data	*	*	*	*	*	*	*	*	*							
Video coding	*	*	*	*	*	*	*	*	*							
6-month data collections end									*	*						

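### Gaze and affect synchrony are each tested at a fixed two-sided 2.5%; this is valid, but Holm's step-down test at the same 5% familywise bound would give modestly more power for the second outcome (optional).

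*Combined protocol and SAP*

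**What the plan says.** Section 3.3 is explicit that there are two: "The two primary outcomes are mother-infant synchronous gaze and mother-infant synchronous affect". Section 4.8.1 compares the arms at 3 months "using a 2.5% type I error rate and two-sided test for our primary outcomes". Section 4.7 sizes the trial on the same basis: "This sample size will achieve 80% power to detect as significant a 0.44 standard deviation difference in primary outcomes", "assuming $\alpha=0.025$ and a 2-sided test", with 100 per arm after 20% attrition.

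Section 4.8.1 gives a Benjamini-Hochberg correction at 5% for groups of related secondary outcomes only. No step-down, ordered or alpha-recycling rule is given for the primary pair. The words Bonferroni and familywise do not appear. That 2.5% applies to each outcome, as half of 5%, is therefore inferred from the number of outcomes and from the power calculation.

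Two further statements bear on any change. Section 4.8.1 foresees several analyses of each outcome: "We will estimate treatment effects with and without key covariates known to be associated with M-I synchrony", and "We will conduct intention to treat (ITT) and per protocol analyses". Section 7.1 adds "We will conduct preliminary analysis on available outcome data at the beginning of years 2 and 3".

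**The concern.** This is a question of efficiency, not an error. A fixed split tests each outcome as if the other result were unknown. Once one null hypothesis is rejected at 2.5%, only one remains, and it can be tested at the full 5% without raising the familywise error above 5%. Holm does this. It rejects everything that the fixed rule rejects and sometimes more, needs no ranking of gaze against affect, and relies on no assumption about their correlation.

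The two rules part in one situation only: one p-value is at most 0.025 and the other lies between 0.025 and 0.05. The fixed rule then calls the second primary outcome negative and Holm calls it positive. This matters here because hypothesis H2 of Aim 1 (section 3.2) predicts improvement in both outcomes, and because power per outcome at the 0.4 SD effect that section 4.7 calls feasible is only about 72%.

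**Working it through.** **Inputs.** From section 4.7: 100 per arm (125 × 0.80); two-sided alpha 0.025; effects of 0.44 and 0.40 SD; and a range of 0.28 to 0.62 from related work. The correlation ρ between gaze and affect is not given; 0 to 0.8 is assumed.

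**1. The plan's own figure.** The test statistic has mean d√(n/2) = 0.44 × √50 = 3.1113. The critical value at two-sided 2.5% is 2.2414. Power = Φ(3.1113 − 2.2414) = Φ(0.8699) = 0.8078. The noncentral t gives 80.2%. The stated 80% reproduces for a single outcome at 2.5%. At two-sided 5% (critical value 1.9600) power would be Φ(1.1513) = 0.8752. At 0.40 SD the two values are 0.7214 and 0.8074.

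**2. Validity of the split.** Familywise error is at most 0.025 + 0.025 = 0.05 under any dependence, and 1 − 0.975² = 0.0494 under independence.

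**3. Where the rules differ, ρ = 0, both effects 0.44 SD.**
- Conclusions differ: 2 × 0.80781 × (0.87520 − 0.80781) = 0.1089.
- Holm power per outcome: 0.80781 + 0.10887/2 = 0.8622.
- Both outcomes: 0.80781² = 0.65256 under the fixed rule; 0.65256 + 0.10887 = 0.7614 under Holm.
- At least one: 1 − (1 − 0.80781)² = 0.9631 under either rule, since Holm's first step is the fixed rule's threshold.

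**4. Over the assumed correlations** (exact bivariate normal probabilities; each cell is fixed → Holm where two values appear):

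| Both effects (SD) | ρ | Per outcome | Both outcomes | At least one | Conclusion differs |
|---|---|---|---|---|---|
| 0.44 | 0 | 0.8078 → 0.8622 | 0.6526 → 0.7614 | 0.9631 | 0.1089 |
| 0.44 | 0.3 | 0.8078 → 0.8566 | 0.6776 → 0.7753 | 0.9380 | 0.0976 |
| 0.44 | 0.6 | 0.8078 → 0.8503 | 0.7096 → 0.7946 | 0.9060 | 0.0850 |
| 0.44 | 0.8 | 0.8078 → 0.8445 | 0.7386 → 0.8119 | 0.8770 | 0.0733 |
| 0.40 | 0 | 0.7214 → 0.7835 | 0.5204 → 0.6445 | 0.9224 | 0.1241 |
| 0.40 | 0.3 | 0.7214 → 0.7774 | 0.5563 → 0.6683 | 0.8865 | 0.1120 |
| 0.40 | 0.6 | 0.7214 → 0.7709 | 0.5988 → 0.6979 | 0.8440 | 0.0991 |
| 0.40 | 0.8 | 0.7214 → 0.7649 | 0.6357 → 0.7227 | 0.8071 | 0.0870 |

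A simulation with t tests on 198 degrees of freedom (200,000 draws, 0.44 SD, ρ = 0.3) gives 0.802 → 0.853 per outcome, 0.669 → 0.770 for both, 0.936 for at least one, and different conclusions in 0.101 of trials.

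**5. Other effect patterns, same method.**
- Both 0.28 SD: per outcome 39.7% → 44.0-44.2%.
- Both 0.62 SD: per outcome 98.4% → 99.0-99.2%; conclusions differ in 1.2-1.7% of trials.
- Effects 0.44 and 0.28 SD: power for the weaker outcome 39.7% → 48.7-50.2%.
- Effects 0.44 SD and zero: power for the real effect 80.8% → at most 81.0%; error on the null outcome 2.5% → 3.9-4.5%. With a real effect of 0.62 SD that error is 4.7-5.0%.
- Both zero: any rejection 4.0-4.9% under either rule.

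**The case against.** The fixed split is a legitimate choice with merits of its own. Each outcome has a 97.5% interval that agrees with its test, and the error on each outcome stays at 2.5% whatever the other shows. Holm gives up both: an outcome significant only by Holm has a 97.5% interval that includes zero, and error on a truly null outcome can approach 5%. These costs are real and are sufficient reason for a sponsor to decline. They do not break the 5% familywise bound.

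The gain is also concentrated in the middle of the effect range. Section 4.7 cites standardised synchrony differences of 0.12 to 0.7, from comparisons of at-risk with normal groups. With both effects at 0.12 SD the rules differ in only 0.9-2.7% of trials, and at 0.7 SD in 0.3-0.4%. That is correct, and it is why the gain is called modest and tied to 0.40-0.44 SD.

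Timing is the strongest practical objection. Protocol V1.6 is dated 31 January 2024 and data collection was projected to end on 31 March 2024 (section 1.2). The documents do not say whether the preliminary analyses of section 7.1 showed synchrony by arm. A success rule relaxed late can look data-driven, so the recommendation has to be conditional.

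Finally, calling the present rule valid covers the alpha split alone. With adjusted and unadjusted estimates and two analysis sets planned, the 5% bound holds only for one designated p-value per outcome. That stands, and it applies to the fixed rule as much as to Holm.

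**Conclusion.** The point holds as an optional efficiency gain at the lowest level of priority. The fixed 2.5% per outcome is a valid split and matches the power section; nothing needs correcting. With both effects at 0.40-0.44 SD, Holm adds about 4 to 6 percentage points of power per outcome and about 7 to 12 points for showing both, and it changes the conclusion in about 7-12% of trials. It does nothing for the chance of at least one positive outcome and almost nothing if only one effect is real.

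The figures rest on 100 analysed per arm, normal test statistics, one designated analysis per outcome, a 5% familywise target that is inferred rather than stated, and an assumed correlation of 0 to 0.8. Holm's validity does not depend on that correlation; only the size of the gain does.

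**What to change.** In section 4.8.1:

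1. Designate one primary analysis per outcome: one intention-to-treat model with a fixed covariate set. Label the other covariate version and the per-protocol analysis as supportive. This is worth doing even if Holm is declined.
2. State a two-sided familywise error of 5% over gaze and affect synchrony, controlled by Holm: the smaller p-value is tested at 2.5% and, only if that is significant, the larger at 5%.
3. Date the change and adopt it only before primary results by arm are seen, and say so. If the preliminary analyses have already shown synchrony by arm, keep the fixed 2.5% as the primary rule and report Holm as supplementary.
4. Say how intervals will be reported, given that a 97.5% interval can include zero for an outcome that is significant only at Holm's second step.

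The power statement in section 4.7 can stay as the conservative single-outcome case. The change needs no more participants and no ordering of the outcomes. Its cost is a short dated amendment, less simple adjusted intervals, and a higher error rate on a null outcome when the other effect is real, within 5%.

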1.3 Flow Diagram

1.4 Schedule of Events for "Randomized Controlled Trial to Improve Mother-Infant Synchrony among Women with Childhood Adversity"

Event / Timepoint & Location	Instruments / Outcome Measures	Recruitment (last trimester)	Baseline (33wks \pm 2wks ga)	Birth (prior to discharge)	Birth (after discharge)	T1 (28 days \pm 7days/+14 days)	T2 (56 days -7 days/+14 days)	T3 (84 days -7 days/+14days)	T4 (6 mos \pm 4 wks)
		Clinics	College of Nursing	TMC, BUMC or Zoom	Phone/text	College of Nursing	College of Nursing	College of Nursing	College of Nursing
Recruitment/Screening		x							
Informed Consent			x						
Randomization				x					
ATVV/Attn Control Training				x	x	x	x	x	
Text Responses (daily)					x	x	x	x	
Text Reminder (monthly)					x	x	x	x	
Phone Call (weekly)					x	x	x	x	
Intervention Fidelity Videos						x	x	x	
REDCap Questionnaires	Screening Questionnaire (phone)	x							
	adverse childhood experiences amb* ACE (phone)	x							
	Demographics Questionnaire		x						
	maternal attachment amb MAAS		x						
	resilience amb BRCS		x				x		
	emotional support amb PROMIS-ES		x				x		x
	stress mindset amb SMM		x				x		
	perceived stress amb PSS-10		x			x	x	x	x
	depressive symptoms amb PHQ-8		x			x	x	x	x
	anxiety amb GAD-7		x			x	x	x	x
	PTSD amb DSM-5 (PCL-5)		x						
	autonomic reactivity amb BPQ-ANS		x					x	x
	parenting received amb PBI-M		x						
	parenting received amb PBI-P		x						
	history of adversity amb ATES		x						
	Childbirth & Infant Survey			x					
	Follow Questionnaire				x	x	x		
	birth experience amb CEQ					x			
	birth experience amb PTSD-childbirth					x			
	parenting amb PSI-SF					x	x	x	x
	Followup Questionnaire at T4								x
	Research Participant Perception Survey								x
Peripheral blood draw	epigenetic marks amb % DNA methylation at CpG sites (n=6)		x			x	x	x	
	OXTR expression amb qRT-PCR of mRNA		x			x	x	x	
	OXTR total protein amb Western Blot		x			x	x	x	
	OXT peptide amb ELISA assay		x			x	x	x	
Infant Saliva	OXT peptide amb ELISA assay					x	x	x	
Mother-Infant Synchrony Videos	Affect Synchrony							x	
	Gaze Synchrony							x	
	Vocal Synchrony							x	
	Touch Synchrony							x	

*amb = as measured by

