3.0 OBJECTIVES AND ENDPOINTS

3.1 Study Overview

We will test the ATVV, a multisensory behavioral intervention, where mothers learn to engage with their infant while administering Auditory (infant directed speech), Tactile (massage), Visual (eye to eye gaze), and Vestibular (rocking) stimulation.⁽²⁴⁾ We build on ATVV's success with preterm infants and their mothers (e.g., improved maternal sensitivity, lower maternal distress, and enhanced infant behavior and development) to determine benefits for full-term M-I dyads.⁽²⁵⁻³⁰⁾ We will target first-time mothers with childhood adversity. Mothers randomized to ATVV will administer it once daily for the first 3 postnatal months. At 3 months, when full-term infants reliably exhibit clear cues and maintain alertness, we will apply a rigorous behavioral measure of M-I synchrony developed by a member of our team using frame-by-frame video of micro-coded M-I behavior quantifying reciprocal speech, touch, gaze, and affect.^(31, 32, 73) Micro-coded behavior yields rich detail of interaction patterns known to influence long-term developmental outcomes.^(7, 18, 19) Our feasibility pilot showed significant and strong correlations between ATVV frequency and improved M-I synchrony over one month.

We will also assess ATVV's effect on maternal and infant peripheral OXT levels,^(7, 19) a known biomarker of M-I synchrony. We, and others, have shown that dampening in the OXT system (i.e., abnormally low OXT blood and saliva levels) is evident in poor M-I synchrony and maternal behavior,⁽³³⁻³⁷⁾ yet little is known about OXT's epigenetic regulation of synchrony or maternal behavior in humans. Thus, we will target regions of the **OXT receptor gene (OXTR)** where DNA methylation is linked to maternal behavior in rodents, psychosocial behaviors in humans, and in our pilot study to M-I synchrony.⁽³⁸⁻⁵²⁾ We will examine whether our OXT measures emerge early to predict efficacy of ATVV and quality of M-I synchrony at 3 months. We analyze maternal blood in pregnancy and at 1, 2, and 3 months post birth (and infant salivary OXT). We aim to identify molecular mechanisms in the OXT system underlying M-I synchrony in maternal blood and discover molecular profiles. Regression based methods assess ATVV effects on and relations among M-I synchrony and OXT measures.

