4.0 STUDY DESIGN

The single-site study design is a 4-year, randomized, two-group, attention-controlled clinical trial. Women (N=250) will be screened for childhood adversity, enrolled in pregnancy to obtain baseline OXT data. Soon after birth (pre-hospital discharge), M-I dyads who continue to be eligible are randomized into the intervention group ($n=125$) and taught to administer the ATVV intervention daily for 3 months or randomized into the attention control group ($n=125$) and taught safe infant care. There are a total of 5 study visits (3rd trimester, soon after birth, 1st postnatal month, 2nd postnatal month, 3rd postnatal month), plus a follow-up phone call at 6 postnatal months to assess quality of parenting using a self-report questionnaire.

This is a randomized controlled trial (RCT) comparing data between the ATVV and Attention Control groups. Random assignment is centrally controlled by our statistician using a computer-generated list of random numbers (0=intervention and 1=control), balanced so that half the M-I dyads are in the ATVV group. Mothers will be asked to not disclose their group assignment to mothers in the postnatal unit.

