4.5 Covariates

We will control for key covariates that may influence outcomes (Table 3). We include a range of instruments to assess psychosocial factors experienced as an adult that may impact the OXT system and parenting behavior.^(39, 110, 112, 128-130) To avoid an OXT spike during/after breastfeeding, we postpone blood draws to > 30-minutes after breastfeeding ends (a valid method used by us and others when studying OXT in breastfeeding mothers).⁽¹³¹⁾ Measuring M-I synchrony < 3 months of age has lower validity, thus we will use the Parenting Stress Index as a valid proxy for quality of parenting^(126,127) expecting it be associated with synchrony.

Table 3. Covariates

Construct	Operational Measure	B /I	1	2	3
Covariates					
Demographics Characteristics	Maternal: health status, age; weight; birth events; return of menses; birth control; mental health history; drug/alcohol use; marital status & father's involvement; education level; income Infant: health status; age; gestational age at birth; infant feeding method; infant's caretakers;				
Maternal Adversity**	Adverse Childhood Experiences (ACE): well-established 10-items on verbal, physical, and sexual abuse; emotional and physical neglect; household challenges (e.g., substance abuse, mental illness, prison). 71% response rate & 93-99% response rate to individual questions. ⁽²⁾ Distribution of scores (N=248,934) ⁽³⁾ 0=38%, 1=24%, 2=13%, 3=9%, $\geq 4=16\%$. Stable over time: test-retest kappa = 0.6-0.7 ⁽¹⁰⁸⁾ Maternal ACE ≥ 2 associated with infant developmental delay (N=311, p<0.05). ⁽¹⁰⁹⁾				
	Adverse Adult Experiences: 8-item modified version of the 10-item ACE providing a similar measure of adversity in adults > 18 years and associated with mental health. ⁽¹¹²⁾				
Maternal Mental Health**	Post-traumatic stress disorder (PTSD): Mini International Neuropsychiatric interview (MINI) Module H, V. 7.0.2 for DSM 5, 2016: 7-items ⁽¹¹³⁾ Concordance between PTSD in MINI versus Structured Clinical Interview for DSM-III-R Patients: Inter-rater reliability kappa=0.78, sensitivity=0.85, specificity=0.96, test-retest kappa=0.73. ⁽¹¹⁴⁾				

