	Depressive symptoms: Patient Health Questionnaire (PHQ-9): 9-items using DSM-IV depression criteria. ⁽¹¹⁵⁾ Scores range 0-27 ⁽¹¹⁵⁾ Diagnostic validity from 8 primary care & 7 obstetrical clinics. Scores > 5 mild symptoms. Scores > 10: 88% sensitivity & 88% specificity for Major Depressive Disorder (MDD). Cronbach's $\alpha=0.86$ & 0.89. Scores ≥ 10 : 7-14 increased odds of MDD diagnosis. ⁽¹¹⁶⁾				
	Anxiety: Generalized Anxiety Disorders (GAD-7): 7-items ⁽¹¹⁷⁾ Scores range 0-21 ⁽¹¹⁷⁾ > 5 mild, > 10 panic disorder, social anxiety & PTSD (66-89% sensitivity & 80-82% specificity). ⁽¹¹⁸⁾ $\alpha=0.89$ in pregnant and non-pregnant. ^(119, 120)				

Parenting Stress**	Parenting Stress Index (PSI-SF): 36-items ^(123,124) 3 domains: parental distress, parent-child dysfunctional interaction, & difficult child. Appropriate from 0 - 3 years. Associated with maternal intrusiveness & sensitivity (elements of synchrony). ⁽¹²⁵⁾ Test-retest=0.85, $\alpha=0.91$. ⁽¹²³⁾			
--------------------	---	--------------------------	--------------------------	--------------------------

*Baseline (B), In-hospital (I), and postnatal months T1, T2, T3; **Available in Spanish

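### The adjusted efficacy estimate conditions on the 1-month Parenting Stress Index, measured after randomisation, and neither the adjusted nor the unadjusted estimate is named as primary

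*Combined protocol and SAP*

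**What the plan says.** Section 4.8.1 states: "We will estimate treatment effects with and without key covariates known to be associated with M-I synchrony". The examples given are mental health, adversity, "infant feeding method, infant health status, and 1-month Parenting Stress Index) which will increase the power of the test". For the behavioural outcomes, which include the two primaries (gaze and affect synchrony), the same section says the method "will be a general linear model regressing the outcome on an indicator for treatment arm". No sentence calls either the adjusted or the unadjusted estimate primary.

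On timing, section 4.0 says that soon after birth, before discharge, "M-I dyads who continue to be eligible are randomized into the intervention group". In the Schedule of Events (section 1.4), the row "parenting amb PSI-SF" is marked at T1, T2, T3 and T4 only, and T1 is nominally day 28. Table 3 in section 4.5 is consistent: it shows three marks for the index, against four for measures that are also taken at baseline.

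On what the index represents, section 4.5 notes that synchrony measured before 3 months has lower validity, "thus we will use the Parenting Stress Index as a valid proxy for quality of parenting", and expects it to be associated with synchrony. Table 3 describes the scale as having "3 domains: parental distress, parent-child dysfunctional interaction, & difficult child".

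**The concern.** Adjustment for a prognostic covariate gains precision without changing the target of estimation when treatment cannot have affected the covariate. Values fixed before randomisation meet that condition by design. The 1-month index does not: by then mothers have had about four weeks of daily ATVV or of control contact.

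The plan's own reasoning makes an ATVV effect on the index plausible. The index serves as an early stand-in for parenting quality, and one of its domains concerns parent-child interaction. Section 3.1 cites earlier ATVV results of "improved maternal sensitivity, lower maternal distress, and enhanced infant behavior and development", although in preterm dyads. The index may therefore be a mediator or an early reading of the outcome.

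If ATVV lowers parenting stress by 1 month, the adjusted gaze and affect estimates would be reduced by the part of the difference that travels with the index. They could miss the 0.025 threshold when the unadjusted estimates pass it. The plan has no rule for which result then stands.

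**Working it through.** **Inputs from the documents.** 100 per arm at 3 months, effect 0.44 SD, power 80% (section 4.7); alpha 0.025, two-sided, for each primary outcome (sections 4.7 and 4.8.1).

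**Assumptions, because the documents give no values.** *a* = improvement in the index due to ATVV, in within-arm SDs, from 0 to 0.4. *r* = size of the within-arm correlation between index and synchrony, from 0.2 to 0.5, with lower stress going with more synchrony. Within-arm SD of synchrony = 1. The index is the only covariate.

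**Step 1: the plan's own figure.** SE = √(2/100) = 0.1414. 0.44/0.1414 = 3.111. Power = Φ(3.111 − 2.2414) = Φ(0.870) = 0.808 (0.802 with the t distribution). The stated 80% reproduces as an unadjusted comparison.

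**Step 2: adding the index.**
- Adjusted effect = 0.44 − a·r
- SE = √[(1 − r²)(2/100 + a²/200)]
- Power = Φ(adjusted effect/SE − 2.2414)

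Example, a = 0.2 and r = 0.3: effect = 0.44 − 0.06 = 0.38; SE = √(0.91 × 0.0202) = 0.1356; power = Φ(2.803 − 2.241) = 0.713.

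Each cell shows adjusted effect (SD) and power, to be read against 0.44 SD and 0.808 unadjusted:

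| a | r = 0.2 | r = 0.3 | r = 0.4 | r = 0.5 |
|---|---|---|---|---|
| 0 | 0.44, 0.825 | 0.44, 0.846 | 0.44, 0.876 | 0.44, 0.912 |
| 0.1 | 0.42, 0.784 | 0.41, 0.786 | 0.40, 0.800 | 0.39, 0.826 |
| 0.2 | 0.40, 0.736 | 0.38, 0.713 | 0.36, 0.699 | 0.34, 0.699 |
| 0.3 | 0.38, 0.681 | 0.35, 0.627 | 0.32, 0.579 | 0.29, 0.540 |
| 0.4 | 0.36, 0.620 | 0.32, 0.534 | 0.28, 0.451 | 0.24, 0.375 |

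Simulation (20,000 trials, ANCOVA t-test) agrees: a = 0.2, r = 0.3 gives effect 0.383 and power 0.714; a = 0.4, r = 0.5 gives 0.241 and 0.370.

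**Step 3: break-even.** Ignoring the small a²/200 term, adjusted and unadjusted power are equal when 0.44 − a·r = 0.44√(1 − r²), so a = 0.44(1 − √(1 − r²))/r. This gives 0.044, 0.068, 0.092 and 0.118 SD for r = 0.2, 0.3, 0.4 and 0.5. Above these values, adjusting for the index costs power.

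**The case against.** The strongest reply is that the total effect is already protected. The unadjusted estimate is planned, the only model written out for gaze and affect has a treatment indicator alone, the sample size reproduces as an unadjusted comparison, and the covariate list is only illustrative. A reader could fairly infer that the unadjusted analysis is the main one. That stands as an inference, and it limits the severity. It does not supply the missing designation or make the power rationale correct for this covariate.

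A second reply is that the table treats the index as the only covariate, whereas the plan would adjust for others too. Suppose one balanced pre-randomisation covariate explains 10% of outcome variance and correlates 0 to 0.5 with the index (both assumed). Break-even against the unadjusted model then rises to about 0.12 to 0.30 SD, and at a = 0.1 the fully adjusted power is 83% to 88%. This is right for that comparison, but the gain comes from the baseline covariate. Alone, that covariate gives SE = √(0.9 × 0.02) = 0.1342 and power Φ(3.280 − 2.241) = 0.850. The decision here is whether to add the index to such a model, and for that contrast break-even is about 0.01 to 0.13 SD, so the low thresholds remain.

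Third, the size of the harm rests on assumed values. The larger shifts approach the full design effect after only one month, and only improvement is tabulated. This also stands. A worsening would push the adjusted estimate above the total effect, which is equally not the quantity wanted. Common causes of the index and synchrony would also prevent the adjusted coefficient from being read as a clean direct effect, although its value is still the total effect minus *a* times the within-arm slope.

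**Conclusion.** The concern holds. The timing and the absence of a primary label are plain in the text. The statement that covariates will raise power is safe for this one only if ATVV leaves the index almost unchanged, within about 0.04 to 0.12 SD for correlations of 0.2 to 0.5. The documents do not show that. The actual loss cannot be stated: over the assumed ranges, the effect of adjusting runs from a gain of about 10 points of power to a fall from 81% to 38%. The unadjusted estimate and the stated sample size are sound.

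This should be fixed before analysis but does not undermine the trial. Mental health, infant feeding method and infant health status have no stated timepoint in section 4.8.1. They carry the same risk only if values recorded after allocation are used.

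**What to change.** In section 4.8.1:

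1. Remove the 1-month Parenting Stress Index from the efficacy model.
2. Limit adjustment covariates to values recorded before randomisation and give the timepoint of each. Candidates already collected are ACE score, baseline depressive symptoms, baseline GAD-7 and gestational age at birth. In-hospital infant health or feeding values qualify only if they are shown to precede allocation; the Schedule of Events puts the birth survey and randomisation in the same column without giving their order.
3. Name one model as primary for gaze and affect, either unadjusted or adjusted for those values, and label the other as sensitivity.
4. Keep the 1-month index as a secondary outcome, in a labelled mediation analysis (section 4.8 already lists mediation tests), or as an auxiliary variable in the imputation, which already draws on all available measures.

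The cost is SAP wording, with no new data and no change to the planned 250. The stated 80% power at 0.44 SD needs no covariate. If ATVV truly does not affect the index, dropping it forgoes about 2 to 10 points of power (0.825 − 0.808 to 0.912 − 0.808), part of which pre-randomisation covariates could recover.
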